6.8 Safety Analysis

Safety endpoints and adverse events analysis will be provided in the Safety population by treatment group as received.

6.8.1 Safety endpoints

- Descriptive tables will be produced by frequency and percentage, for the presence of each ocular unusual sensation UPON INSTILLATION at least one time during the study (for each ocular unusual sensation UPON INSTILLATION)
- Descriptive tables will be produced by frequency and percentage, for each ocular unusual sensation UPON INSTILLATION and by mean (SD) for the total score for the 6 predefined symptoms at Day 8, Day 35 and Day 84.
- The total score for the 6 predefined symptoms will be compared between treatment groups using Student T-test, if data have normal distribution. If it is not the case, Mann-Whitney Wilcoxon test will be used.

Note: For the analysis of ocular unusual sensation UPON INSTILLATION, usual severity, usual duration and frequency will be set to 0 if the patient felt no ocular unusual sensation upon instillation or if the severity is equal to 0 (absent).

- Far best-corrected visual acuity (in logMAR) at Selection visit, Day 35 and Day 84 will be described by mean (SD) for the worst eye and for the contralateral eye. The frequency distribution will be also presented in /10 (1/10, 2/10 to 10/10, >10/10);
- Tolerance assessment by the investigator and by the patient at Day 35 and Day 84 will be described in 4 classes and in 2 classes (Very satisfactory or satisfactory, not very satisfactory or unsatisfactory). The treatment groups for 4 classes description will be compared using a Cochran-Mantel-Haenszel (CMH) test.

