6.8.1.2.5 Tear Break-Up Time (TBUT)

The TBUT will be done at each visit in each eye. The value at Day 1 will be the baseline value.

The tear break-up time will be measured three times during the first minute after the instillation of one drop of fluorescein. The TBUT value analysed will be the sum of the three measurements.

6.8.1.2.6 *Conjunctival hyperaemia using Mac Monnies photographic scale*

The conjunctival hyperaemia will be assessed using the Mac Monnies photographic scale in each eye ([Figure 9](#)). The value at Day 1 will be the baseline value.

Figure 9 **Mac Monnies photographic scale**

6.8.1.2.7 *Ocular symptoms*

Patient will be asked:

“How do you judge the severity of your following ocular symptoms **WITHIN THE LAST 48 HOURS?**”

*« Comment jugez-vous la sévérité de vos symptômes oculaires suivants ressentis **DANS LES DERNIERES 48 HEURES?** »*

The severity of the following ocular symptoms (global evaluation for both eyes) will be assessed at each visit: **burning/irritation, stinging/eye pain, itching, eye dryness feeling, foreign body sensation, light sensitivity and fluctuating blurred vision** as follows:

- (0) = Absent;
- (1) = Mild, Present but not disturbing;
- (2) = Moderate, Disturbing, but not limiting daily activities;
- (3) = Severe, Very distressing and interfering with daily activities.

6.8.1.2.8 *Ocular symptoms upon instillation:*

Patient will be asked: “Have you felt any unusual sensation upon instillation since the last visit?”

« Avez-vous ressenti une gêne/sensation oculaire inhabituelle à l’instillation depuis la dernière visite ?»

If the answer is yes, a table regrouping the functional ocular signs will have to be completed. Ocular symptoms upon instillation at Day 8 (optional), Day 35 and Day 84: Burning/irritation, stinging/eye pain, itching, eye dryness feeling, foreign body sensation, light sensitivity and other symptoms will be graded by the subject according to the following severity scale and with their duration:

- (0) = Absent;

- (1) = Mild, Present but not disturbing;
- (2) = Moderate, Disturbing, but not limiting daily activities;
- (3) = Severe, Very distressing and limiting with daily activities.

6.8.1.2.9 *Performance assessment by the investigator*

The evaluation of the IMD performance will be assessed by the investigator, using the following rating scale:

- Very satisfactory;
- Satisfactory;
- Not very satisfactory;
- Unsatisfactory.

6.8.2 **Safety measures**

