2 STUDY DESIGN

2.1 Overview

This is a multicentre, randomised study, investigator-masked, 2 parallel groups (T2259 versus Vismed® Multi) of 38 evaluable patients each.

The patients were randomised after a run-in-period of 7 to 10 days with preservative free artificial tears (Hydrabak®, one drop in each eye 3 to 6 times daily). Then, they were treated with either T2259 or the reference product (Vismed® Multi) for 84 days (\pm 7 days).

Investigation visits were performed as following:

Day 1-10/Day 1-7	Selection visit (Visit 1)
Day 1	Randomisation/ Inclusion visit (Visit 2)
Day 8 (\pm 1)	Visit 3 Optional Visit (if the investigator and/or the patient thinks it is necessary)
Day 35 (\pm 3)	Visit 4
Day 84 (\pm 7)	Final visit (Visit 5)

The Visits V2, V3, V4 and V5 should have been performed at the same hour (± 4 hours).

Reclassification of visits:

All “premature withdrawal” visits will be reclassified as decided in BR Meeting. Number of days between premature withdrawal visits and randomisation visit will be calculated and depending of this number of days, visits will be reclassified to the nearest planned non-missing visit.

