4.3 Changes to statistical information in the clinical trial protocol

In the protocol, the final visit form can either be D84 visit or Withdrawal visit. Withdrawal visits specified in the final visit form will be reviewed during the BR meeting and reclassified to the closest missing planned timepoint (D8, D35 or D84).

Information collected during withdrawal visit will be used in the analysis as reclassified visit.

In the protocol, for the primary performance endpoint, the investigator site and the investigation product-by investigator site interaction was expected to be explored as a secondary analysis prior to presenting the final model. As the number of randomised patients by site is low, investigator site will not be tested but replaced by country effect.

For the primary performance endpoint, additional sensitivity analysis will be performed: Mixed Model for Repeated Measures (MMRM) model will be used including: treatment group, baseline value, visit, treatment group by visit interaction and treatment group by baseline value interaction.

To investigate the bias of recruitment before and after the recruitment interruption, patients will be classified without or with possible impact of COVID-19 pandemic based on their screening visit date respectively up to and including 18 MARS, or after the 18-MAR-2020. Descriptive analysis will be performed according to this variable (populations, countries, premature withdrawal, protocol deviations and demographic characteristics (age and sex). Moreover, for the primary endpoint, an exploratory model will be performed using initial model, adjusted on this new variable.

For the analysis of previous and concomitant medications, ATC level 2 and 4 will be used, instead of level 3 and 4 specified in the protocol.

For performance and tolerance assessment, Wilcoxon signed-rank test will be replaced by Cochran-Mantel-Haenszel (CMH) test, and Chi-2 test for Dry Eye Symptoms will be replaced by Cochran-Mantel-Haenszel (CMH) test.

In the safety endpoints, for the comparison between treatment group of the total score of the 6 predefined symptoms (unusual sensation upon instillation), Student T-test will be performed, instead of the use of Analysis of Covariance (ANCOVA) analysis as specified in the protocol. Student T-test will be performed if the normality of the data is verified. If the data have not normal distribution, Mann-Whitney Wilcoxon test will be used.

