5.3 Multiple Imputations for Handling of Dropouts or Missing data

Treatment Emergent Adverse Events (TEAEs) are AEs that occurred after the first IMD instillation. AEs that occurred the day of the first IMD instillation will be reviewed in detail to identify if AEs appeared before or after the first treatment with IMD (to decide if they have to be considered as TEAEs or not). If no additional information is available, they will be treated as TEAEs.

By default, AEs will be considered as TEAEs if no enough information is available.

For primary analysis performed on FAS, Last Observation Carried Forward (LOCF) method will be applied in case of missing value.

In order to define the type of treatments (previous, concomitant or post-study) and treatment duration, partially start/end dates will be imputed with the following rules for calculations:

For treatment start date:

- If only the day is missing, it will be considered as 1st for calculations
- If only the year is completed, day and month will be considered as January 1st for calculations

For treatment end date:

- If only the day is missing, it will be considered as the last day of the month for calculations
- If only the year is completed, day and month will be considered as December 31st for calculations

If the date is totally missing, it will not be replaced.

Other missing data will not be replaced.

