6.2 Disposition of Patients

Descriptive statistics will be provided. No statistical test will be performed.

- Study dates: first date and last date will be provided for selection visit, inclusion visit and last visit (visit 5 or early withdrawal).
- Number and percentage of patients in each country and each site will be provided in FAS and Safety set.
- Status of patients:
 - Among all patients: number and percentage of patients selected and not selected, reason if not selected (as reported by the investigator at the selection visit)
 - Among selected patients: number and percentage of patients who attended inclusion visit, number and percentage of patients included and not included, reason if not included (as reported by the investigator on end-of-study page: Adverse event, lack of performance, withdrawal by subject, lost to follow-up, screen failure, other)
 - Among included patients: randomised (Yes, No)
 - Among randomised patients: number and percentage of patients with visits done (for each visit: Yes, No), visit type if Visit 5 done (Day 84 +/-7 days, Premature discontinuation visit), has the patient completed the study (Yes, No), reason if study not completed (Adverse event, lack of performance, withdrawal by subject, lost to follow-up, screen failure, other)

Non-selected patients, non-included patients and early withdrawals will be individually listed.

Note: In case of withdrawal, withdrawal visit will be re-assigned depending to the date of withdrawal. The withdrawal visit will be re-assigned to the closest planned missing visit (D8, D35 or D84). All re-assigned withdrawal visits will be discussed during BR and recorded in the BR meeting minutes.

- Analysis sets:
 - From randomised patients: Number and percentage in safety population, number and percentage of patients excluded from safety population and reason(s) for exclusion
 - From safety population: Number and percentage in FAS, number and percentage of patients excluded from FAS and reason(s) for exclusion
 - From FAS: Number and percentage in PP, number and percentage of patients excluded from PP and reason(s) for exclusion
 - Number and percentage of patients with major and minor protocol deviations, globally and for each section of deviation (inclusion criteria deviation, exclusion criteria deviation, randomisation, visit windows and chronology, run-in treatment compliance, IMD compliance, primary performance endpoint and secondary efficacy endpoints, other), in FAS.

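### Tolerance ratings of patients who leave within about three weeks without the optional Day 8 visit enter no tolerance comparison, and the Day 35 instillation score mixes two recall windows

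*SAP*

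**What the plan says.** **Withdrawal visits.** Under Protocol 6.7.3 a patient who stops early has all final-visit assessments. Under Protocol 6.4.5 these include tolerance by patient and investigator, visual acuity and the instillation questions. SAP 4.3 has such visits "reclassified to the closest missing planned timepoint (D8, D35 or D84", and adds: "Information collected during withdrawal visit will be used in the analysis as reclassified visit". SAP 6.2 repeats the rule and sends each case to the blind review. SAP 2.1 states something different: "visits will be reclassified to the nearest planned non-missing visit".

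**Tolerance and acuity.** SAP 6.8.1: "Tolerance assessment by the investigator and by the patient at Day 35 and Day 84 will be described". The four-class rating is compared by a CMH test. Acuity is described, without a test, at selection, Day 35 and Day 84. SAP 5.3 gives rules for the primary endpoint in the FAS, for adverse event status and for partial treatment dates, then closes: "Other missing data will not be replaced".

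**Instillation symptoms.** Protocol 6.8.1.2.8 asks: "Have you felt any unusual sensation upon instillation since the last visit". SAP 6.8.1 tabulates the symptoms and their total score at Day 8, Day 35 and Day 84, and states: "The total score for the 6 predefined symptoms will be compared between treatment groups using Student T-test, if data have normal distribution". A further table shows whether each sensation occurred at any time in the study.

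**The concern.** A patient who skips Day 8, stops on day 12 because the drops sting and is rated unsatisfactory has a complete withdrawal assessment. The visit rule files it under Day 8, and no tolerance table or test uses Day 8. Whether an early bad rating counts then depends on attendance at an optional visit. By contrast, the primary endpoint has LOCF and a mixed model to use early data.

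For instillation, two patients with identical stinging in week 1 only can get different Day 35 scores. The one who skipped Day 8 reports it at Day 35. The one who attended has already reported it, and SAP 3.3 sets all six symptoms to 0 at a visit with none reported. The Day 35 comparison treats the two scores as the same quantity.

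Safety is part of the secondary objective, and Protocol 6.1 cites the related lower-strength product as better tolerated than Vismed. A tolerance comparison from this trial may therefore be quoted.

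**Working it through.** **1. Where a withdrawal visit goes.** Protocol 6.4.3 puts the Day 8 visit 6 to 8 days after randomisation (nominally 7). Protocol 6.4.4 and 6.4.5 put the next visits at 35 and 84 days. The boundaries of the closest-missing rule are the midpoints:

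- Day 8 and Day 35: (7 + 35)/2 = 21 days, or (8 + 35)/2 = 21.5 if Day 8 is taken as 8 days.
- Day 35 and Day 84: (35 + 84)/2 = 59.5 days.

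For a patient with no Day 35 visit:

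| Withdrawal (days after randomisation) | Day 8 skipped | Day 8 attended |
|---|---|---|
| 1 to 20 | Day 8 | Day 35 |
| 21 | Day 8, or a tie with Day 35 | Day 35 |
| 22 to 59 | Day 35 | Day 35 |
| 60 to 83 | Day 84 | Day 84 |

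Only the cells marked Day 8 lose the tolerance rating. Acuity values in those cells also leave the descriptive tables.

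**2. The conflicting rule in SAP 2.1.** Read literally, nearest non-missing sends an attendee who leaves on day 12 to Day 8, and gives a non-attendee no post-randomisation visit to go to. It does not rescue the rating.

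**3. Possible size for tolerance (all rates assumed).** SAP 5.1 gives 101 randomised, so about 50 per arm. Let w patients in one arm leave within three weeks, all rated unsatisfactory, with 90% of the others satisfied and a share a of the w having attended Day 8.

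- Satisfied among all 50: 0.9(50 − w)/50.
- Satisfied among those in the Day 35 table: 0.9(50 − w)/(50 − w + a·w).

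With w = 5 the numerator is 0.9 × 45 = 40.5:

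- all patients: 40.5/50 = 81%;
- a = 0: 40.5/45 = 90%, a gap of 9 points;
- a = 0.6: 40.5/48 = 84.4%, a gap of about 3 points;
- a = 1: 40.5/50 = 81%, no gap.

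With a = 0 the gap is 0.9w/50: 3.6, 5.4, 9.0 and 14.4 points for w = 2, 3, 5 and 8.

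**4. Instillation.** If a share p of an arm has sensations in week 1 only and a share q of these attends Day 8, Day 35 records p(1 − q). For p = 20% that is 20, 15, 10, 5 and 0% at q = 0, 25, 50, 75 and 100%. With the same q in both arms the absolute difference shrinks by the factor (1 − q) and the ratio is unchanged. The ratio changes only if attendance differs by arm.

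**The case against.** The best reply is that early intolerance remains visible elsewhere, and much of this stands.

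- Instillation symptoms are tabulated at Day 8, and a withdrawer moved to Day 8 enters those tables. The any-time table shows every reported sensation.
- SAP 6.8.2 tabulates adverse events leading to device withdrawal, related events and events by severity. Withdrawal reasons are shown for all randomised patients.
- Day 35 and Day 84 are the protocol's own tolerance timepoints, and the non-inferiority conclusion is untouched.

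None of this restores the comparison. Day 8 attendees are a self-selected group. The any-time table gives presence only, with no severity and no test. Adverse event tables contain no tolerance ratings. Blind review looks at each reassignment, but nothing tells it to keep these ratings.

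A reader might go further and infer that a real difference disappears. Suppose early stinging in 40% and 20% of the arms, with Day 8 attended by 60% and 20% of those affected. Day 35 then shows 0.40 × 0.40 = 16% against 0.20 × 0.80 = 16%. That needs attendance to differ by arm, and Day 35 to be read alone: on the same figures the any-time table shows 40% against 20%. The two mechanisms also pull apart, since attending Day 8 exposes the instillation score to the shorter window but keeps a later tolerance rating.

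Nor do the documents say that irritation is common or that discomfort triggers Day 8. Protocol 4.2 expects irritation to be very unusual, the comparator leaflet calls such effects rare, and Protocol 6.4.3 makes the visit depend only on whether investigator or patient thinks it necessary.

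**Conclusion.** The concern holds for the tolerance and instillation comparisons, not for the safety evaluation as a whole. Under SAP 4.3 and 6.2, ratings from a withdrawal within about 21 days without a Day 8 visit enter no tolerance comparison, and the Day 35 instillation score has no common recall window. If such withdrawals are more frequent in one arm, the tolerance table flatters that arm.

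The size cannot be derived, because the documents give neither the number of early withdrawals nor Day 8 attendance. Under the assumed rates with five such patients, the overstatement of satisfaction runs from 9 points with no Day 8 attendance to none with full attendance. The change is worth making before unblinding.

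**What to change.** In SAP 6.8.1:

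- **Tolerance.** Beside the Day 35 and Day 84 tables, compare patient and investigator tolerance at each patient's last available post-baseline rating. Include the withdrawal-visit rating at its actual date, even if the drops had already been stopped. Describe acuity the same way.
- **Instillation.** Add a between-group comparison of each patient's worst total score over Day 1-35: the maximum of any Day 8 record, withdrawal record by Day 35, and Day 35 record. Keep the by-visit tables, and state that Day 8 attendees contribute more reports.
- **Population.** Run both in the Safety population as SAP 6.1.2 defines it (at least one administration). The derived flag in SAP 3.3 needs a treated-eye record at Day 35 or Day 84 and, depending on how that record is keyed, could drop early withdrawers.
- **Visit rule.** Reconcile SAP 2.1 (nearest non-missing) with SAP 4.3 and 6.2 (closest missing).

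The cost is SAP wording and a few tables from data already collected. A worst score gives no time course, which the by-visit tables still provide.

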6.8.2 Adverse events

The adverse events were coded using the MedDRA dictionary version 22.0.

Treatment-emergent AEs (TEAEs) will be defined as AEs with onset date on or after the first day of the IMD instillation. If the AE onset date is not available, AEs will be considered as TEAEs by default.

Ocular and systemic AEs will be analysed separately on the basis of the localisation as recorded by the investigator in the CRF, i.e., localisation = Right eye, Left eye or Both eyes for ocular TEAEs, and localisation = Other for non-ocular TEAEs.

The number and percentage of patients experiencing at least one TEAE will be provided by treatment group, overall by MedDRA primary SOC and PT, for the following categories of adverse events:

- All TEAEs;
- Non-serious TEAEs;
- Treatment related TEAEs (i.e. related or missing relationship with the IMD);
- Serious TEAEs;
- TEAEs leading to medical device withdrawal.
- TEAEs by severity
- TEAEs by relationship with the IMD

Note: Results will be provided by descending frequency (for SOCs and for PTs within SOC, for the whole population analysed).

Individual patient data listings of AEs will be performed for overall AEs, SAEs and SADEs, separately for ocular and systemic AEs. The following variables will be presented:

- Treatment group,

- Patient's identifier,
- Worse eye (right eye / left eye)
- Dry eye aetiology
- Gender,
- Age at baseline (Day 1),
- Diagnosis (verbatim),
- SOC,
- PT,
- Localisation,
- Date / time of occurrence,
- Time to occurrence (days) from the date of the first IMD instillation,
- Treatment-emergence
- Date / time of recovery / date of death, if any,
- Duration (days),
- Outcome,
- Frequency and details,
- Severity,
- Action taken regarding the IMD,
- Requirement for therapy adjustment / modification,
- Requirement for surgical / medical procedure,
- Seriousness,
- Relationship with the IMD in the investigator's opinion,
- Relationship with protocol procedure.

Listings will be sorted by treatment group, patient's identifier and date of onset.

The Individual data listing will present all CRF items and calculated variables as TEAE (Yes/No), time between first instillation of the study and the start date, time between first instillation and stop date, duration of the adverse event.

Listing of Deaths, Other Serious adverse events, discontinuations due to adverse events and other adverse events of special interest will be also provided for narratives.

Discontinuations due to adverse events include drug related AE leading to premature IMP drug OR study withdrawal (i.e. drug related AE with action taken = drug withdrawn OR End of study with premature discontinuation due to this AE) will be listed.

Patient data listings of COVID-19 AEs (PT: COVID-19, Coronavirus infection) will also be produced.

Individual patient data listings of non-emergent AEs will be performed on the SAF population, separately for ocular and systemic AEs.

A excel file with relevant information will also be performed for the CSR narrative.

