6.7.3 Criteria and procedures for patient withdrawal or discontinuation

Patient should be withdrawn from the investigation if, in the opinion of the investigator, there is any situation or condition which puts the subject at significant risk. Any patient may voluntarily discontinue the investigation at any time he or she chooses (Declaration of Helsinki), without prejudice. The investigator may choose to discontinue a patient for reasons related to the investigation product (AE or unsatisfactory therapeutic response). In either event, details should be recorded in the e-CRF and reported separately.

Possible reasons for withdrawal include the following:

- AEs leading to discontinuation from the investigation;
- Treatment failure: the patient or the physician does not feel that the IMD has adequately relieved his/her symptoms;

In case of aggravation of dry eye syndrome or superficial keratitis, an adverse event form must be completed by the investigator and all the investigations planned at the final visit must be done (premature withdrawal visit). The investigator will prescribe the best appropriate treatment to the patient.

- Patient's request;
- Other reason.

If the patient is lost to follow-up, the investigator must contact his/her patient to obtain more information (by phone, fax, regular mail or email...).

If a patient discontinues prematurely the investigation, the investigator will perform all the investigations planned at the final visit and will prescribe the best appropriate treatment to the patient.

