14.1.4 Relationship with the Investigational Medical Device

The investigator will assess the causality/relationship between the IMD and the AE and record that assessment in the e-CRF based on the following definitions (only one answer possible):

1 RELATED: The adverse event is related to the IMD and cannot be reasonably explained by others factor (e.g., concomitant therapy, patient condition, and/or other intervention);

2 NOT RELATED: A simultaneous disease, a simultaneous treatment or any other known cause is clearly responsible for the adverse event.

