HLA-DR at Day 1 and Day 84	LBHLAREL2=LBHLAREL If LBYN="Y" And LBVAL="N" Then LBHLAREL2=.	HLA-DR positive cells (% , missing for invalid result)	Numeric (8.1)
Tolerance assessment by the investigator at Day 35 and Day 84	IF TOLERI In ('SATISFACTORY' 'VERY SATISFACTORY') Then TOLERI2=1 If TOLERI In ('NOT VERY SATISFACTORY' 'UNSATISFACTORY') Then TOLERI2=2 This derivation rule is valid for Days 35 and 84	Tolerance assessment by the investigator	1="Very satisfactory / Satisfactory" 2="Not very satisfactory / Unsatisfactory"
AE start date, AE end date	AEDUR=(AEENDT – AESTDT)+1 only if AEOUT=" RECOVERED/RESOLVED"	AE duration (in days)	Numeric (8.1)
AE start date, Start date of treatment	AETIME=(AESTDT – DAKDATD1)	AE onset from First IMD instillation (days)	Numeric (8.1)
Start date of treatment / Time of onset of AE	If AESTDT < DAKDATD1 then TEAE=0 If AESTDT >= DAKDATD1 then TEAE=1 In case of missing or uncompleted onset date/time, the status will be defined during the Blind Review (BR) meeting according to the information recorded in other fields	Treatment Emergent Adverse Event (TEAE)	0="No" 1="Yes"
AE type and localisation	If TEAE=1 And localisation in ("BOTH EYES" "RIGHT EYE" "LEFT EYE") Then OCTEAE=1 If (TEAE=1 And AELOCLAT="OTHER") Or TEAE=0 Then OCTEAE=0	Ocular TEAE	0="No" 1="Yes"
AE type and causality	If TEAE=1 And AEREL="RELATED" Then ADE=1 If TEAE=0 Or (TEAE=1 And AEREL="NOT RELATED") Then ADE=0	ADE	0="No" 1="Yes"
AE type and serious event	If ADE=1 And AESER = "Y" Then SADE=1 If ADE=0 Or (ADE=1 And AESER="N") Then SADE=0	SADE	0="No" 1="Yes"
AE type and Action Taken with Study Treatment	If TEAE=1 And AEACN "drug withdrawn" Then WTEAE=1 Else WTEAE=0	TEAE leading to Medical Device withdrawal	0="No" 1="Yes"

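### The adverse-event discontinuation listing that feeds the narratives is limited to drug-related events, against the unrestricted wording elsewhere in the plan

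*SAP*

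**What the plan says.** SAP section 6.8.2 first announces the output: listings of deaths, other serious events, "discontinuations due to adverse events and other adverse events of special interest will be also provided for narratives". No causality condition is attached. It then defines the discontinuation part: "Discontinuations due to adverse events include drug related AE leading to premature IMP drug OR study withdrawal", spelled out as "drug related AE with action taken = drug withdrawn OR End of study with premature discontinuation due to this AE".

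Elsewhere, withdrawal because of an adverse event is an all-causality category. Protocol section 7.3.4 and the list of event categories in SAP section 6.8.2 both ask for treatment-emergent events leading to withdrawal of the product, whatever the cause. SAP section 3.3 derives the matching flag, labelled "TEAE leading to Medical Device withdrawal", from "AE type and Action Taken with Study Treatment", with no relatedness term. Tables 6.17 and 6.18 in SAP section 8.1 report it for ocular and systemic events.

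Protocol section 6.7.3 says how worsening is to be recorded: "In case of aggravation of dry eye syndrome or superficial keratitis, an adverse event form must be completed by the investigator". It also requires the final-visit examinations at that point. Protocol section 14.1.4 allows two causality codes. RELATED means that the event "cannot be reasonably explained by others factor (e.g., concomitant therapy, patient condition, and/or other intervention"). NOT RELATED means: "A simultaneous disease, a simultaneous treatment or any other known cause is clearly responsible for the adverse event".

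**The concern.** A discontinuation listing shows, patient by patient, who stopped because of an adverse event. Relatedness is a judgement that belongs in a column of such a listing, where a reader can weigh it. Used as an entry condition, it removes cases before anyone sees them.

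In this trial the condition bears on an important kind of event. Every randomised patient has dry eye disease, so an investigator who sees keratitis worsen can always consider the disease as the explanation. Patient condition is also one of the factors that the protocol names as speaking against a RELATED code. Withdrawals for worsening are relevant both to safety and to lack of effect, and a complete discontinuation listing should contain them. At stake is the completeness of that listing and of the narratives written from it.

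**Working it through.** No arithmetic applies, so the check sets the rules side by side.

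**Step 1: is the restriction binding?** The verb in the definition could be read as open-ended. The explanatory clause closes that reading, because it states the operating rule and makes drug-relatedness part of it. The second route, study exit, refers back to the same drug-related event. Both routes, device withdrawal and study exit, are therefore filtered.

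**Step 2: does worsening attributed to disease fail the rule?** Protocol 6.7.3 makes it an adverse event. Under Protocol 14.1.4, an event for which the disease is judged clearly responsible is coded NOT RELATED. It then fails the definition in SAP 6.8.2 even if it ended treatment or participation.

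**Step 3: where does such an event still appear?** Take a treatment-emergent event in a patient who leaves the study early.

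| Output | RELATED, action coded drug withdrawn | NOT RELATED, action coded drug withdrawn | NOT RELATED, study exit for the event, action coded otherwise |
|---|---|---|---|
| Discontinuation listing (SAP 6.8.2) | yes | **no** | **no** |
| Table 6.17 or 6.18 | yes | yes | no |
| Listing 7 or 8 (all treatment-emergent events) | yes | yes | yes |
| Listing 1 (early withdrawals) | yes | yes | yes |
| Table 1.6a (reasons for withdrawal) | yes | yes | yes |

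SAP 6.8.2 gives action taken and relationship to the device as variables of the event listings, so both facts can be read there. If the event is also serious, it reaches the narratives through the serious-event part of the same sentence. The gap in narrative material therefore concerns non-serious events coded NOT RELATED.

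**Step 4: is the listing among the planned outputs?** SAP 8.2 names Listings 1 to 15. They cover early withdrawals, protocol deviations, aetiology, treatments, dose regimen, OSI, treatment-emergent events, serious events, serious device effects, non-emergent events and COVID-19 events. None is a listing of discontinuations due to adverse events. The text of 6.8.2 and the output list do not agree.

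**Step 5: is a reason given?** SAP 6.8.2 gives none for the narrower rule, and SAP 4.3, which sets out changes from the protocol, does not mention it.

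**The case against.** The strongest reply is that little follows from the restriction. A reader might infer that withdrawals for worsening are hidden. The documents do not support that: the table above shows them in several outputs with no causality filter, and Tables 6.21 and 6.22 show events by relationship. This part of the reply stands in full.

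A reader might also infer that the non-inferiority comparison is weakened. It is not. Lack of performance is a separate end-of-study reason in SAP 6.2. Withdrawal visits are reassigned to the closest missing planned visit and used in the analysis (SAP 4.3 and 6.2). The FAS analysis with LOCF can use the value at withdrawal (SAP 6.7.1). Staining measured when a patient leaves for worsening can thus enter the confirmatory FAS analysis, and nothing there depends on this listing.

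A third tempting step is to call the device-withdrawal flag in SAP 3.3 defective because it ignores study exit. The flag matches its own label and the category in Protocol 7.3.4 and SAP 6.8.2, so widening it would be a preference. The case in the last column of the table also needs a patient to leave because of an event whose action was not coded as drug withdrawn. The e-CRF coding rules are not in the documents, so how often that could happen is unknown.

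Finally, NOT RELATED requires another cause to be clearly responsible. An uncertain case fits neither code cleanly, and nothing shows how investigators would code worsening keratitis. That is right, and it limits the point to events actually coded NOT RELATED.

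None of this explains why a listing announced without a causality limit should be defined with one.

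**Conclusion.** The point holds as a small, definite fault in the SAP. The rule in 6.8.2 yields an incomplete discontinuation listing and contradicts both the sentence that announces it and the all-causality withdrawal category used elsewhere. Every discontinuation for an event coded NOT RELATED is omitted from that listing. The number of patients cannot be derived from the documents and could be zero.

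The consequence stops at the listing and the narratives built on it. The safety tables, the general event listings, the disposition outputs and the primary analysis are unaffected.

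This rests on two assumptions: that the explanatory clause is programmed as written, and that at least some worsening events would be coded NOT RELATED. SAP 6.8.2 also mentions an Excel file for narratives but does not give its selection rule, so it cannot be counted on to fill the gap.

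**What to change.** In SAP 6.8.2, delete the drug-related condition in both places in the definition, so that the listing contains every adverse event leading to device withdrawal or study withdrawal. Show relationship to the device as a column. Add the listing to SAP 8.2.

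Leave the device-withdrawal flag in SAP 3.3 as it is. The corrected listing will cover study exits due to an adverse event.

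The cost is a change of SAP wording, one listing to program from variables that the event listings and the end-of-study page already hold, and possibly a few more narratives. No new data collection is needed.
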